Obsessive-compulsive disorder (OCD) is a disabling psychiatric disorder characterized by recurrent uncontrollable and unwanted thoughts (obsessions), and repetitive behaviors in response to those obsessions (compulsions). The lifetime prevalence of OCD is 2-3% [1], and the time-consuming symptoms often interfere with all aspects of daily life. Moreover, population-based studies have shown that OCD is associated with academic underachievement across the lifespan [2] and with substantial labor market marginalization, including higher risk of receiving disability pension, being on long-term sickness absence, and long-term unemployment [3].

One of the recommended first-line treatments for OCD is individual cognitive behavioral therapy (CBT) that includes exposure and response prevention (ERP). In CBT, patients are exposed to situations that trigger obsessions while actively refraining from performing compulsions. Although it is an effective treatment with 65% of participants responding to treatment [4], CBT typically requires weekly sessions during at least 3 months [5]. This extensive time-frame requires significant effort and persistence from patients and increases the risk of dropout. Moreover, a substantial proportion of patients remain impaired even among those who complete the treatment.

In response to this, several condensed formats of CBT have been developed in various countries. Amongst them is the Bergen 4-Day Treatment (B4DT), developed in Norway. In this treatment, patients receive intensive CBT at the clinic for 4 consecutive days. B4DT has been shown to achieve response rates over 90% when delivered in regular care in several uncontrolled treatment trials, and one randomized controlled trial (RCT) that used waitlist and self-help as controls [6]. However, it has yet to be compared to the gold standard CBT.

In this non-inferiority RCT, we will test the efficacy of B4DT compared to gold standard CBT. If B4DT turns out to be non-inferior to traditional CBT, the range of evidence-based options will be broadened and patients may be able to achieve clinically meaningful improvements within a shorter period of time.

Research questions

The overall approach of this study is to directly compare the intensive Bergen 4-day treatment (B4DT) to gold-standard individual cognitive behavior therapy (CBT) for adults with OCD.

Primary outcome

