The primary outcome is OCD severity as assessed by the blind rater-administered Yale-Brown Obsessive-Compulsive Scale (Y-BOCS). Specifically, we will test whether B4DT is non-inferior to

standard CBT 14 weeks after treatment start. The non inferiority margin is set to 4 points on the Y-BOCS.

Non-inferiority designs test whether a novel treatment is not unacceptably less efficacious (in this case, 4 points) than another treatment whose efficacy has already been established. However, a non-inferiority study may also be used to test for superiority without inflating the false-positive rate [7]. We will therefore sequentially test 1) whether B4DT is non-inferior to gold standard CBT , and 2) whether B4DT is superior to gold standard CBT.

Secondary outcomes

Our secondary objectives are to compare B4DT and gold standard CBT with regards to:

- 1) Time to response. We hypothesize that B4DT, due to its intensive design, will provide a faster response than gold- standard CBT. A comparison of the proportion of treatment responders at week 4 and week 7 will be used to test this hypothesis.
- 2) Rates of response and remission. The proportion of participants in response and remission will be compared 14 weeks after treatment start. For these outcomes, we have no directed hypotheses.
- 3) Dropout rate. We will test whether the proportion of patients that discontinue treatment prematurely (i.e., complete less than 50% of the treatment) differs between the B4DT and the gold standard CBT arm. For this outcome, we have no directed hypothesis.
- 4) Cost-effectiveness. Health economic data will be collected using clinic data on therapist usage and the Treatment Inventory of Costs in Psychiatric Patients [11]. Between-group costs will be calculated and compared 14 weeks after treatment start. The emphasis will be on cost-effectiveness analyses using responder status as outcome and health-care provider as the cost perspective. For this outcome, we have no directed hypothesis.
- 5) Negative effects. The total score of the Negative Effects Questionnaire will be compared 14 weeks after treatment start, as well as the prevalence of severe adverse events. For this outcome, we do not have a directed hypothesis.

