Patients in this arm will receive an intensive treatment delivered mostly in group format, the Bergen 4-day treatment (B4DT) [6]. The group sizes will be 3-6 participants with a 1:1 patient to therapist ratio. In the week leading up to the intensive part of the treatment, participants will have two scheduled phone/video calls with a therapist to assess readiness and encourage participants to prepare relevant exposure tasks. Day 1 of the intensive treatment includes psychoeducation about the rationale for exposure with response prevention (ERP), and deciding on exposure tasks. Days 2 and 3 focus on individually tailored and therapist-assisted ERP in as many relevant settings as possible (up to 7 hours of ERP per day). In the evenings, patients should continue with self-guided ERP and may receive therapist support via text messages or phone calls on demand. In the afternoon of day 3, patients can invite relatives and friends to a psychoeducation session. Day 4 of the intensive treatment focuses on treatment summary and relapse prevention, as well as planning self-guided ERP for the upcoming 3 weeks. After 14 weeks, participants have individual follow-up sessions at the clinic where they summarize their experiences after completing treatment. There is no ERP during this session.

All groups will be led by a therapist with expertise in B4DT. All therapists will have participated in the Norwegian OCD-training program [12] or have documented equivalent training. Prior to participation, all therapists will have participated in at least two B4DT groups.

Individual CBT

Patients will receive 16 90-minute sessions of individual CBT for OCD with an emphasis on ERP, delivered over a time period of 14 weeks according to a validated protocol [10]. Sessions will be held twice weekly at a specialist clinic during the first 2 weeks and once a week for the remaining 12 weeks. Sessions 1-2 contain psychoeducation about OCD and CBT, goal setting, and planning of ERP exercises. Sessions 3-14 include therapist-guided ERP (at the clinic, in the patients' homes or elsewhere as needed) with planned self-practice ERP between sessions. Sessions 15-16 contain a summary of the treatment and lessons learned, as well as relapse prevention and planning of continued self-practice ERP.

Therapist competence and adherence

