The primary outcome measure is the blind assessor-rated Y-BOCS, which will be administered at pre-treatment, at weeks 4 and 7 during treatment, 14 weeks after treatment start (primary endpoint), and at the 7- and 16-month follow-ups [21]. Blinded assessors will undergo training prior to conducting clinician-rated assessment and practice on videos of OCD case examples. In order to be allowed to conduct assessments for the project, the assessors will have to deviate no more than 1 point on single items, no more than 2 points on the obsessions subscale and the compulsions subscale and no more than 4 points on the Y-BOCS total score compared to expert raters at the two clinics. Inter-rater reliability on the Y-BOCS will be reported.

Secondary clinician-administered outcome measures are the Clinical Global Impression – Severity and Improvement (CGI-S, CGI-I), the Patient Exposure/Response Prevention Adherence Scale (PEAS), the Structured Clinical Interview for DSM-5 for OCD and related disorders (SCID-5) and the Mini International Neuropsychiatric Interview. SCID-5 and MINI will be administered at pre-treatment to confirm the OCD-diagnosis and assess comorbidities

Secondary self-rated outcome measures are the Obsessive-Compulsive Inventory-Revised (OCI-R), self-rated Y-BOCS, Montgomery-Åsberg Depression Rating Scale—Self-Rated (MADRS-S), Work and Social Adjustment Scale (WSAS), Assessing Quality of Life 6 Dimensions (AQoL-6D) (for economic evaluation), Credibility/Expectancy Questionnaire (CEQ), Working Alliance Inventory—Short Form Revised (WAI-SR), the TIC-P resource use questionnaire (for economic evaluation), and the Negative Effects Questionnaire (NEQ). Participants will also rate their treatment preference measured on a 7-point Likert-type scale (pre-treatment and post-treatment).

Table 2. Assessments of secondary outcomes at different time points

	Pre-treatment	Week 4	Week 7	Week 15 (primary end-point)	7-month follow-up	16-month follow-up
Clinician-rated instruments						
SCID-5 (OCD)	X					
MINI	X					
Y-BOCS	X	X	X	X	X	X

CGI-S	X	X	X	X	X	X
CGI-I		X	X	X	X	X
PEAS*		X	X	x		
Self-rated instruments						
YBOCS-SR	X			X	X	X
OCI-R	X			X	X	X
MADRS-S	X			X	X	X
WSAS	X			X	X	X
AQoL-6D	X			X	X	X
TIC-P	X			X	X	X
NEQ				X	X	X
Other adverse events		X	X	X	X	X
CEQ**		X				
WAI-SR**		X				
Treatment preference	X			X		

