To explore whether B4DT leads to a faster treatment response than individual CBT, the proportion of responders in the two treatments will be compared 4 weeks after treatment start. The 95% confidence intervals of the odds ratio of response will be calculated for this purpose. Because the B4DT-group will have received their full treatment dose at the point of assessment while the gold standard CBT-group will have received only about 25%, there are strong reasons to believe that, from this perspective, B4DT will lead to faster symptom relief. An identical analysis will be conducted at 7 weeks to evaluate whether there is a difference between the treatments when participants in the individual CBT group have received 50% of the treatment.

Rates of response and remission

The proportion of participants in response and remission will be compared 14 weeks after treatment start. Response is defined as a reduction of 35% or more on the Y-BOCS and a CGI-I score of 1 or 2. Remission is defined as a Y-BOCS score of 12 or less and a CGI-S score of 1 or 2. Proportions will be compared using a two-sided two-proportions z-test.

Dropout rate

To explore whether the groups differ in terms of treatment completion, we will compare whether the proportion of patients that discontinue treatment prematurely differs between B4DT and gold standard CBT. A dropout will be defined as a patient in the B4DT arm that participates in less than 1.5 full days at the clinic, or a patient in the gold standard CBT arm that participates in less than 8 CBT sessions. Proportions will be compared using a two-sided two-proportions z-test.

Negative effects

To describe negative treatment effects, a two-sample t-test will be used to compare the total NEQ-scores at the primary endpoint (scores on the subscales will be presented in the supplement). The additional semi-structured questions about suicidal behaviors and thoughts, hospitalization, deterioration of psychiatric symptoms, and psychiatric care outside the study, will be reported in a frequency table.

Cost effectiveness

Health economic data will be collected using the self-rated Treatment Inventory of Costs in Psychiatric Patients (TIC-P) questionnaire [11]. The TIC-P records costs for the past month

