(pretreatment) or the past 14 weeks (post-treatment and follow-up), and costs will be extrapolated to cover the entire period between assessments when needed. Costs from third party payer (including only intervention costs), healthcare, and societal perspectives will be analyzed in relation to clinical efficacy (responder status; cost-effectiveness analysis) and quality-adjusted life-years on the AQoL-6D (QALYs; cost utility analysis). Additional cost-effectiveness analyses will use remitter status as outcome. The economic analysis will be conducted using multiple imputation of missing values. Cost data and QALYs will be analyzed using generalized linear models (GLM) to allow for the consideration of other distributions and functional forms to fit the cost and outcome data [24]. Total costs will be analyzed while controlling for baseline costs. Total QALYs will be analyzed while controlling for baseline AQoL-6D utility values [25].

A micro costing framework will be used to estimate the cost of delivering the interventions prospectively. Intervention costs will include the therapists' time to deliver sessions, as well as any training needed. Healthcare resource use will be costed using national pricelists, and medication costs using market prices, and estimated by multiplying frequencies of resources used by unit costs. Unit costs for resources related to social support and assistance will be sourced from published sources or based on authors' own estimates. Productivity losses will be estimated using the human capital approach [26]. Productivity losses due to absenteeism from paid work will be the product of the number of days off from work by individuals due to mental illness by the average hourly salary rate in Sweden [27] including social fees. Losses due to absenteeism from unpaid work will be the product of the number of days not performing unpaid work by the estimated hourly cost of leisure time [28]. Productivity losses related to reduced efficiency at work will be estimated in the same fashion as productivity losses due to absenteeism, but additionally multiplied by a weighed score representing how the illness impacted the participants' productivity [29].

Additional outcomes used for quality assessment

Therapist competence and adherence

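### The post-treatment TIC-P recall is exactly as long as the interval it must cover, so a form completed a few days late can miss patient-reported costs of the B4DT clinic days

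*Combined protocol and SAP*

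**What the plan says.** The Cost effectiveness section defines two recall periods for the self-rated TIC-P. At baseline, "The TIC-P records costs for the past month". Afterwards it covers "the past 14 weeks (post-treatment and follow-up), and costs will be extrapolated to cover the entire period between assessments when needed". The extrapolation method is not stated, and the recall is not tied to a calendar date.

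The timing of the first post-baseline form is given in two ways. The Measurements text puts the primary assessment at "14 weeks after treatment start (primary endpoint"), and the list of secondary outcomes says "Between-group costs will be calculated and compared 14 weeks after treatment start". The column of Table 2 in which the TIC-P is ticked is headed "Week 15 (primary end-point"). No visit window is given. Table 2 has no TIC-P at week 4 or week 7.

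The arms differ in when patients attend. In B4DT, "patients receive intensive CBT at the clinic for 4 consecutive days", preceded by telephone or video contact: "In the week leading up to the intensive part of the treatment, participants will have two scheduled phone/video calls". The plan does not say whether those calls count as treatment start. In the comparator, "Patients will receive 16 90-minute sessions of individual CBT for OCD with an emphasis on ERP, delivered over a time period of 14 weeks".

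Delivery of both treatments is costed separately, from clinic data on therapist use and prospective micro-costing. The economic emphasis is on the health-care provider perspective. The third-party-payer analysis uses intervention costs only. The societal analysis adds losses from paid and unpaid work.

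**The concern.** A look-back of 14 weeks placed 14 weeks after treatment start has no slack. Each day of delay in completing the form removes one day from the front of the treatment interval. B4DT attendance is concentrated in four days at that front, while CBT attendance is spread over the whole interval. The same delay can therefore remove most or all of one arm's attendance and very little of the other's.

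The plan's other provisions do not obviously repair this. The baseline form looks back before treatment. The 7-month form, also with a 14-week recall, starts at about week 16.4 (7 months is about 30.4 weeks; 30.4 − 14 = 16.4). Multiple imputation does not apply to a form that was completed. Labelling secondary results exploratory deals with power and multiplicity, not with an error that has a direction.

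At stake is the societal cost comparison. Days away from paid or unpaid work during the B4DT block could go uncounted, which would make B4DT look cheaper than it is to patients and employers.

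**Working it through.** **Inputs from the documents.** Recall of 14 weeks = 98 days; primary assessment at 14 weeks (day 98, counting treatment start as day 0) or Week 15; B4DT on 4 consecutive days; CBT twice weekly for 2 weeks, then weekly for 12.

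**Plan's own figure.** 2 × 2 + 12 × 1 = 16 CBT sessions, as stated.

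**Assumptions.** Treatment start is the first B4DT clinic day, so the block is days 0–3. CBT sessions fall on days 0, 3, 7, 10, then weekly from day 14. The recall is applied to the day. Extrapolation is proportional scaling.

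**Formula.** A form completed on day 98 + k looks back to day k. Attendance before day k is lost. Scaling multiplies what remains by (98 + k)/98.

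| Form on day | k | B4DT days lost | CBT sessions lost | B4DT days after scaling | CBT sessions after scaling |
|---|---|---|---|---|---|
| 98 | 0 | 0 of 4 | 0 of 16 | 4.00 | 16.00 |
| 99 | 1 | 1 of 4 (25%) | 1 of 16 (6.25%) | 3.03 | 15.15 |
| 100 | 2 | 2 of 4 (50%) | 1 of 16 | 2.04 | 15.31 |
| 101 | 3 | 3 of 4 (75%) | 1 of 16 | 1.03 | 15.46 |
| 102 | 4 | 4 of 4 (100%) | 2 of 16 (12.5%) | 0 | 14.57 |
| 105 | 7 | 4 of 4 | 2 of 16 | 0 | 15.00 |

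Days 103 and 104 lose the same attendance as day 102.

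**Week 15 read as the fifteenth calendar week (days 98–104), completion spread evenly.**
- B4DT: (0 + 0.25 + 0.50 + 0.75 + 1 + 1 + 1)/7 = 0.64.
- CBT: (0 + 3 × 1/16 + 3 × 2/16)/7 = 0.08.
- The average loss is therefore about 64% against 8%.

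**Start counted from the first preparatory call.** If that call is 7 days before the block, the block is days 7–10, and a day-105 form, which looks back to day 7, loses 0 of 4. If the call is 5 days before, it loses 2 of 4; if 3 days before, 4 of 4.

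**Can scaling other absence make up the difference?** The form asks about all days off, so absence unrelated to treatment is scaled too. At day 105 the scaling adds 7/98 of the reported days. Adding back 4 days this way needs 4 ÷ (7/98) = 56 days of other absence within the 98.

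**Which costs are exposed?** Therapist time and training do not come from the TIC-P, so the loss of delivery cost is zero in both arms. What remains is other health-care use in the first days and, mainly, absence from paid and unpaid work.

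**The case against.** Several stronger conclusions are tempting, and the documents do not support them.

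- *A late form drops the cost of the B4DT block.* It does not. Delivery cost comes from clinic data and micro-costing. The payer analysis is untouched, and the emphasised health-care perspective could lose only other care used in the first days.
- *Any delay loses the whole block.* Total loss needs at least four days; one to three days lose a quarter to three quarters.
- *Table 2 builds in a seven-day delay.* CBT fills weeks 1 to 14, so Week 15 may simply be the calendar week that opens at 14 elapsed weeks, which agrees with the text. The form is self-rated, and its completion day need not be that of the assessor visit.
- *Extrapolation cannot restore the loss.* No method is stated. Proportional scaling is an assumption, and it gives partial relief through other absence, although 56 such days would be needed for full relief.

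Other points limit the size. The questionnaire itself is not reproduced, and a recall equal to the treatment interval may be meant to reach treatment start. Patients may well report a memorable four-day treatment that falls just outside the period. The plan counts days off due to mental illness, and whether treatment days are reported that way is unknown. The documents do not give the share of participants in work, so no change in societal cost or in cost-effectiveness can be calculated.

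All of this stands as a limit on size and certainty. It does not remove the mismatch: the stated recall has no margin, completion time is not controlled, and under a literal reading the error falls far more heavily on one arm.

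**Conclusion.** The point holds, conditionally, and is minor. If treatment start is the first clinic day, forms completed 1–3 days after day 98 miss 25–75% of the B4DT clinic days, and forms completed 4–7 days after miss all of them, against 1–2 of 16 CBT sessions. Under a calendar-week reading of Week 15 the average is about 64% against 8%. With start set at a call seven days before the block, a day-105 form loses nothing.

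The direction is to understate B4DT's patient-reported cost. If 90-minute CBT sessions are never reported as days off, the error is still one-sided, because CBT then has nothing to lose. The conclusion rests on literal recall, on treatment days being reported as illness absence and, for the scaling result, on proportional extrapolation.

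A reader might infer that the cost-effectiveness results as a whole are biased. The documents do not support that: the exposure lies mainly in the secondary, exploratory societal analysis, and the primary non-inferiority conclusion is not involved.

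**What to change.** 1. In both arms, anchor the post-treatment TIC-P to a date pre-filled by staff: *since your first treatment day on dd/mm*. Define first treatment day so that the whole B4DT block is included.
2. State in the Cost effectiveness section that extrapolation applies only to periods that no form covers, and give the method.
3. Reconcile Week 15 in Table 2 with 14 weeks after treatment start in the text.

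The cost is one line on the questionnaire and a few sentences in the plan. The downside is a recall period a few days longer when a form is late.

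Costing attendance time from clinic records is optional. It adds an item that the plan does not list, and it should be used only if the form tells patients to leave treatment days out, so that they are not counted twice.

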This study was designed to have high power to test the primary hypothesis, that B4DT is non-inferior to gold standard CBT using a 4-point margin on the Y-BOCS. However, this study is not sufficiently powered to make confirmatory claims based on the results of the secondary analyses. This means that the results will be interpreted as explanatory (despite the fact that 95% confidence intervals of group differences will be reported to follow common practice in the field).

Methods

Study Design

We will conduct a single-blind (blinded outcome assessors), randomized (1:1), controlled non-inferiority trial comparing intensive 4-day CBT and gold-standard individual CBT for adults with OCD. The total number of participants will be 120 (60 per group). Participants will be assessed before treatment start, at week 4 and 7, 14 weeks after treatment start (primary end-point), and 7- and 16-months after treatment start (follow-ups). The Consolidated Standards of Reporting Trials (CONSORT) flow chart of the trial is shown in Figure 1. The study is pre-registered at XYZ (no. 123). Hypotheses were specified in advance. This process included determining outcome scales, statistical models and cut-offs, time-points of evaluation, and publishing analysis scripts before the beginning of data collection. During the trial, we will follow Good Clinical Practice (GCP) and all quality- and safety aspects will be regularly monitored by an external party, the Karolinska Trial Alliance (i.e. case by case monitoring of informed consent, inclusion/exclusion criteria, source data quality, and adverse events). The study has been approved by the Swedish Ethical Review Authority (EPM 2022-01713-01) and Helse Bergen HF (no. 490097).

CONSORT 2010 Flow Diagram

[figure not shown]

Figure 1. CONSORT-flow diagram. Abbreviations: B4DT, Bergen 4-day treatment; CBT, cognitive behavior therapy.

Participants

Patients referred to one of the two involved OCD specialist clinics in Stockholm and self-referred patients will be assessed for eligibility by a staff clinician during a full psychiatric assessment. Candidates that live within approximately one hour of both clinics and match the inclusion/exclusion criteria (see Table 1) will be offered participation in the study and asked to provide informed consent.

Table 1. Overview of inclusion and exclusion criteria

Inclusion criteria	≥ 18 years of age.
	Primary diagnosis of OCD according to DSM-5.
	Clinician-rated Y-BOCS score of ≥ 16

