Abbreviations: AQoL-6D, Assessing Quality of Life 6 Dimensions; CEQ, Credibility/Expectancy Questionnaire; CGI-I, Clinical Global Impression–Improvement; CGI-S, Clinical Global Impression–Severity; MADRS-S; Montgomery–Åsberg Depression Rating Scale–Self-Rated; MINI, Mini International Neuropsychiatric Interview; NEQ, Negative Effects Questionnaire; OCI-R, Obsessive–Compulsive Inventory–Revised; PEAS, Patient Exposure/Response Prevention Adherence Scale; SCID-5, Structured Clinical Interview for DSM-5 Disorders; TIC-P, Treatment Inventory of Costs in Psychiatric Patients; WAI-SR, Working Alliance Inventory–Short Form Revised; WSAS, Work and Social Adjustment Scale; Y-BOCS, Yale–Brown Obsessive Compulsive Scale; Y-BOCS-SR, Yale–Brown Obsessive Compulsive Scale–Self-Rated; Other adverse events, semi-structured questions about potential severe adverse events and psychiatric care outside the study

* PEAS rated once at the last day of B4DT treatment

** CEQ and WAI-SR rated by participants at the last day of B4DT treatment and week 2 in individual CBT

Treatment-response will be defined as a $\geq 35\%$ reduction on the Y-BOCS and a Clinical Global Impression–Improvement (CGI-I) score of 1 ("very much improved") or 2 ("much improved"). Remission will be defined as a score of ≤ 12 on the Y-BOCS and a Clinical Global Impression–

Severity (CGI-S) rating of 1 ("normal, not at all ill") or 2 ("borderline mentally ill"). Recovery will be defined as a sustained remission status at the long-term follow-ups[8].

Safety and adverse events

Data on adverse events including suicidal ideation, and initiation of additional psychiatric care, will be collected at each assessment following inclusion, as well as through the regular contact between participants and therapists during treatment. A standardized self-rated questionnaire (Negative effects questionnaire, NEQ; [9]) containing 32 questions about incidents and negative effects will be used at the primary endpoint and follow-ups.

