If a participant expresses suicidal ideation during treatment or at subsequent assessments, assessors will initiate a structured suicide risk assessment in accordance with routines at the clinic. If there is an urgent need for psychiatric care, a trial psychiatrist will contact participants to schedule an appointment as soon as possible. Serious adverse events (e.g., urgent psychiatric care or discontinued treatment due to a worsening of psychiatric symptoms) will be described in detail on a case-by-case basis.

Statistical analysis

All analysis scripts have been uploaded to a public repository with the analysis strategies described in detail using simulated data (<https://osf.io/w5bfp/>).

Primary outcome

Y-BOCS

The primary non-inferiority hypothesis on the clinician-rated Y-BOCS will be evaluated using ANCOVA of group differences at post-treatment with pre-treatment score as covariate. It will be based on participants that have received at least 50% of the treatment (i.e., attended at least 8 sessions of individual CBT or 1.5 days of B4DT) and completed the post treatment assessment 14 weeks after treatment start. This per protocol approach is chosen to avoid potential problems related to study design that can bias the results towards the alternative hypothesis of non-inferiority (the opposite is true in superiority trials). No data imputation will be conducted at this stage. A 95% confidence interval will be used to model the gold standard CBT-B4DT effect. Non-inferiority will be considered supported if the upper bound is less than 4 (the non-inferiority margin) and superiority will be considered supported if the upper bound is less than 0. This testing procedure has the Type I error rate controlled at the 2.5% level for both comparisons.

For sensitivity assessment, the same ANCOVA model will be used again but with an intention to treat approach. Missing data will then be estimated using maximum likelihood after which the models are refitted. The aim of these steps is to address the potential influence of non-random missing data in the primary per protocol analysis.

Non-inferiority margin

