All patients will get either gold standard CBT or B4DT delivered by clinicians who are specialized in each of these forms of treatment delivery. Gold standard CBT is already the firsthand choice for this patient group, and its efficacy and safety has been demonstrated by several studies of high quality [4]. While B4DT has not yet been evaluated in an RCT with an active control group, it is an intensive face-to-face treatment built on ERP. Moreover, uncontrolled studies have suggested that the effect is similar or improved compared to gold standard CBT [6]. We therefore consider the additional risks associated with participating in the B4DT-arm to be small. All participants will be monitored closely during the study and additional treatment will be provided in case of severe deterioration. Such decisions will be made on a case-by-case basis by the clinicians. This means that if a patient becomes significantly worse during treatment, he/she will be handled in the same way as the regular patients at the clinic.

The requirement to travel to another specialist clinic within Stockholm may put a strain on some participants who have financial or mobility difficulties or simply do not wish to travel. Participants referred to the clinics by other health-care services and who decline participation in the trial or turn out not to be eligible, will have an equal chance to receive specialist treatment at the clinic they were assessed. Excluded self-referred participants will be guided to adequate care.

Maximizing knowledge gain and minimizing risk of bias

Systematic evaluations of clinical trials have in recent years highlighted limitations in current practice that bias the scientific literature [14, 15, 16, 17]. As researchers and other stakeholders have begun to acknowledge the need to better control different sources of bias, the interest in issues related to replicability, transparency, and error control have grown substantially in

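### Scores obtained after additional treatment stay in the per-protocol primary analysis and in its sensitivity analysis, which can pull the result towards non-inferiority if the arm doing worse receives more of it

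*Combined protocol and SAP*

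**What the plan says.** Under Statistical analysis, Primary outcome, the non-inferiority ANCOVA is based on "participants that have received at least 50% of the treatment" (8 CBT sessions or 1.5 B4DT days) who also completed the 14-week assessment. There is no third condition. The stated reason for this set is to avoid design problems that "can bias the results towards the alternative hypothesis of non-inferiority". The section adds: "This testing procedure has the Type I error rate controlled at the 2.5% level for both comparisons". The sensitivity analysis refits the same ANCOVA by intention to treat, with maximum likelihood for missing data.

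Under Ethics and dissemination, Patient safety, participants are monitored and "additional treatment will be provided in case of severe deterioration". Clinicians decide case by case, and patients who worsen are managed like the clinic's other patients. The arms are treated at two different clinics (Randomization and concealment).

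Under Safety and adverse events, data on adverse events, including suicidal ideation and "initiation of additional psychiatric care, will be collected at each assessment following inclusion". The analysis section puts psychiatric care outside the study in a frequency table (Negative effects). The exclusion of other planned psychological treatment for OCD in Table 1 is an entry criterion.

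**The concern.** Nothing in the plan removes a patient from the per-protocol set because of additional treatment, sets the later score aside, or names such treatment as a deviation or intercurrent event. The Primary outcome and Patient safety sections are therefore not reconciled in the analysis.

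In a non-inferiority comparison this matters when the less effective arm has more deterioration and so more additional treatment. Its week-14 mean then improves for reasons other than the randomised treatment, and a true inferiority can be hidden. The schedule gives B4DT more room for this. A B4DT patient meets the 50% rule after 1.5 days and finishes the intensive part in 4 days, leaving about 13 weeks before the endpoint. A CBT patient is in trial therapy for most of that time.

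The ITT analysis deals with missing scores. These scores are observed, so it keeps them, and no stated analysis would show the effect.

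**Working it through.** **Inputs from the documents.** 60 per arm with 10% missing, so 54 per arm; pre-treatment mean 22.6 (SD 3.78); CBT post-treatment mean 12.9 (SD 4.07); margin 4; one-sided error 2.5%.

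**Assumptions, because the documents give no figure.** Pre-post correlation r = 0.3; normal scores with the same SDs in both arms; B4DT truly worse by 4 points; additional treatment triggered by the same rise over the pre-treatment score in both arms; a gain of 3 to 6 Y-BOCS points by week 14. The difference is taken as B4DT minus CBT, so positive means B4DT is worse.

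**1. The plan's own figure.** Without covariate gain, SE = 4.07 × √(2/54) = 0.783. Power at no true difference = Φ(4/0.783 − 1.96) = Φ(3.15) = 99.9%, consistent with the stated >95%. That figure is not in dispute.

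**2. Who would be treated.** The SD of change is √(3.78² + 4.07² − 2 × 0.3 × 3.78 × 4.07) = 4.65. Mean change is 12.9 − 22.6 = −9.7 in CBT and −9.7 + 4 = −5.7 in B4DT. The share at or above trigger k is 1 − Φ((k + 9.7)/4.65) in CBT and 1 − Φ((k + 5.7)/4.65) in B4DT.

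**3. Effect on the test.** Shift = (B4DT share − CBT share) × gain. ANCOVA SE = 4.07 × √(1 − 0.3²) × √(2/54) = 0.747. False non-inferiority rate = Φ(−1.96 + shift/0.747).

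| Trigger | CBT treated | B4DT treated | Gain 3: shift, rate | Gain 6: shift, rate |
|---|---|---|---|---|
| 4 points or more | 0.16% | 1.85% | 0.051, 2.9% | 0.101, 3.4% |
| 2 points or more | 0.59% | 4.89% | 0.129, 3.7% | 0.258, 5.3% |
| any worsening | 1.85% | 11.01% | 0.275, 5.6% | 0.550, 11.0% |

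Of 54 B4DT patients this is about 1.0, 2.6 and 5.9 treated. Simulating the ANCOVA gives about 3%, 4-6% and 6-12%. For example, a 2-point trigger with a gain of 5 gave an estimated difference of 3.78 and a rate of 4.8%. Over correlations of 0, 0.3 and 0.5 and gains of 5 or 10 points, the simulated rate ran from 2.6% to 33%.

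**4. Direction.** The second simulation, also at r = 0.3, treats a fixed share of the worst patients in each arm.
- Equal shares (5% or 10% in both arms) left the mean difference at about 4.0, with rates of 3.4% to 4.8%. The rate still exceeds 2.5% because lowering the worst scores also shrinks the residual SD.
- With 5% in B4DT and none in CBT, rates were 4.6%, 6.4% and 12.5% for gains of 3, 5 and 10.
- With none in B4DT and 5% in CBT, they were 1.6%, 1.2% and 0.5%.

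**The case against.** Keeping every score whatever further care was given is a legitimate treatment-policy choice. The same sentence on additional treatment covers both arms, and decisions are made case by case at two clinics, so the direction cannot be known in advance. Severe deterioration should be rare: even with B4DT worse by 4 points, only about 1.9% of its patients would end 4 or more points above baseline. Additional care may be urgent psychiatric care, which need not lower the Y-BOCS. Care outside the study is tabulated, and serious adverse events, including urgent psychiatric care, are described case by case. The public analysis scripts may say more; they are not part of the documents and were not checked.

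Most of this stands, and it limits the size and certainty of the effect. It does not close the gap. The plan does not state a treatment-policy choice, and its reason for the per-protocol set points the other way. A frequency table shows how often care was given, not what it did to the confidence bound.

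A reader might infer that the plan as written does bias the trial towards non-inferiority, and by a large amount. If 10% of B4DT patients and no CBT patients gain 9.7 points, the shift is 0.97 and the rate is Φ(−1.96 + 0.97/0.783) = 23.5%. The documents do not support that. It sets additional treatment in CBT to zero, treats nearly as many B4DT patients as the 11% expected to worsen at all, and credits each with the whole mean improvement of a full CBT course (22.6 − 12.9 = 9.7).

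**Conclusion.** The gap is real: scores after additional treatment enter both the primary analysis and its sensitivity analysis, and nothing stated tests their influence. The effect can go towards non-inferiority and does so if the worse arm receives more additional treatment. It is about neutral for the mean difference if use is equal, and it reverses if CBT receives more. Under the assumptions above, the false non-inferiority rate is about 3% when only a 4-point worsening leads to treatment, 4-6% for 2 points and 6-12% for any worsening, against the nominal 2.5%. With a trigger as strict as the word severe suggests, the lower end is more plausible. The rates of use and the gains are assumptions throughout.

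A separate effect runs the other way: CBT patients who stop before session 8 because of worsening leave the set, which favours CBT. It is not included in these figures.

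**What to change.** Leave the care and the primary set unchanged, and say in the SAP that the primary analysis keeps these scores. Pre-specify one sensitivity ANCOVA. For anyone in either arm with additional psychiatric or OCD treatment recorded before week 14, replace the week-14 score with the worst of three values: the pre-treatment score, the last Y-BOCS before that treatment began, and the observed week-14 score. Report counts and timing by arm. Describe non-inferiority as robust to additional treatment only if this upper bound is also below 4. As an added condition it cannot raise the false-claim rate.

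Simply carrying the last earlier score forward is not enough. Y-BOCS is taken only at weeks 4, 7 and 14 after the pre-treatment assessment. A B4DT patient who relapses after week 7 would keep a good week-7 score, and early CBT scores reflect only part of the treatment (about 25% at week 4 by the plan's own account). Both favour B4DT.

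The cost is SAP wording and one more model; the start of additional care and the interim Y-BOCS are already collected. The downsides are a more conservative check that the trial might not pass, and a single imputed value, treated as observed, for a few patients. If a deterioration peaked between assessments, the check recovers only part of the shift. This is a cheap improvement.
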